IRB00097529

NCT03795753

Determining the benefits of improving communication in BPAP/CPAP users

Principal Investigator: [name]

Date 03/27/2019

Minimal Risk Protocol

- 1. Protocol Title
- 2. Objectives
- 3. Background
- 4. Study Design
- 5. Study Population
 Number of Subjects
 Inclusion and Exclusion Criteria
 Inclusion
 Exclusion
 Vulnerable Populations
 Setting
 Recruitment Methods
 Consent Process
 6. Procedures
 7. Data and Specimens
- 8. Data Analysis
- 9. Privacy, Confidentiality and Data Security
- 10. Risks and Benefits
 - Risks to Subjects

Adverse events

Potential Benefits to Subjects

11. Disclosures

References

1. Protocol Title

Determining the benefits of improving communication in BPAP/CPAP users

2. Objectives

The purpose of this study is to determine the effectiveness of a non-invasive communication aid for BPAP/CPAP masks. This study also looks to determine the potential impact of the device on patients with obstructive sleep apnea (OSA) and the individuals that interact with the device.

The hypothesis is as follows: The non-invasive communication aid for patients receiving BPAP/CPAP therapy will deliver clear and effective communication between the patient and medical personnel. Furthermore, the device will increase the patient's efficacy at communicating with others.

3. Background

Non-invasive positive pressure ventilation (NIPPV) is a crucial tool used to treat respiratory distress and failure, especially in acute exacerbations of COPD. ¹ Approximately 15-24 million US citizens have COPD. ^{2,3} Of these patients, acute exacerbations of COPD accounted for almost 700,000 hospitalizations in 2010, and are expected to increase annually. Exacerbations are dangerous - with mortality rates ranging from 2.5% to 28%, depending on severity - and expensive - with costs contributing to the \$32.1 billion spent annually on COPD. ^{3,4}

Current medical practice acknowledges that treating respiratory distress and preventing respiratory failure is a paramount concern. Given the nature of the NIPPV mask, communication impairment is a commonly accepted sacrifice to maintain a patient's respiratory condition. Anecdotally, the history and physical examination of a new patient comprises the majority of the data gathering necessary for making medical decisions. Communication is critical to providing context.

However, there is a growing body of work that indicates that limited communication can both increase length of stay and readmission rates. We can extrapolate such information from studies of communication limitations due to language barriers. For patients with language barriers, a 3-year retrospective study indicated that the absence of a professional interpreter on just admission and discharge alone significantly increased length of stay by 1.5 days and readmission rates by 63% (absolute increase 9.4%). ⁵

We will therefore study the benefit that improved communication can provide for patients on

NIPPV.

4. Study Design

This is a single-blinded, randomized control trial.

The device tested will be referred to as a "communicator".

Every patient will be consented. If accepted, we will proceed. Each patient's partner will also be consented. Demographics, including age, race, duration of BPAP/CPAP therapy, will be collected at this time.

Block randomization will be used with variable block sizes of three and six. This guarantees that the 2:1 ratio is closely maintained throughout the trial. Sealed envelopes will be utilized, with "disable" being the placebo and "enable" being the treatment. The subjects are numbered from 1 to 42. If we randomize only 30 subjects, we will have 20 enable and 10 disable. If we have 30 subjects, then the power is 70%.

One interim analysis will be undertaken after fifteen subjects are evaluated for the primary prepost outcome. The O'Brien-Fleming stopping rule will be used with a Type I error rate of 0.05.

Based upon the randomization envelope, we will randomize patients to the communicator or no-communicator arm. The study consenter will turn the device on if randomized to the

Version Date: 27 Mar 2019

communicator and disable the device if randomized to the no-communicator arm. In both situations, the device will appear outwardly similar (i.e. power lights will still appear to be on).

The study will be conducted in three phases:

- without the mask on, and
- with the mask on and without the communicator attached, and
- with the mask on and with the communicator attached.

We will recruit patients with both full face mask and nasal mask.

All patients will be issued a single-use hose and full face mask for the duration of the study. Mask fit will be determined by standard templates.

For all patients for the duration of the trial, we will provide a constant pressure of 10 cm H2O when on NIV.

We may, at our discretion, provide the CPAP/BPAP machine for the duration of the study.

The study coordinator will first instruct the patient on the study protocols. The patient and the partner will be seated a pre-specified distance from each other in a room. The patient and partner will be informed that the entire session will be recorded, and the microphone will be placed close to the partner. A speaker playing standard ICU background noises at a fixed volume will be placed near the patient. ⁶

A list of single words and 5-word through 15-word sentences will be provided to the patient. Each single word may be read aloud up to two times. The partner must then select the read word out of a list of twelve possible words. Each sentence may be read aloud up to two times. The partner must transcribe each sentence on a standardized form. A survey will be provided to

Version Date: 27 Mar 2019

evaluate the "mask off" period.

The patient will then put on the BPAP/CPAP mask, without the communicator attached.

Patients will be asked to speak normally with the same volume and effort they used when they were speaking without the mask on. Patients will have a trial period where they can read through single words and sentences. During this period, a study coordinator may show a sign to remind patients that they should not speak louder or overpronounce and overenunciate words.

A list of single words and 5-word through 15-word sentences will be provided to the patient. Each single word may be read aloud up to two times. The partner must then select the read word out of a list of twelve possible words. Each sentence may be read aloud up to two times. The partner must transcribe each sentence on a standardized form. A survey will be provided to evaluate the "mask on, communicator off" period.

The communicator will then be attached to the BPAP/CPAP mask. The study coordinator will either enable or disable the communicator, based on the randomization arm. A new list of single words and 5-word through 15-word sentences will be provided to the patient. The protocol will remain the same. Each single word may be read aloud up to two times. The partner must then select the read word out of a list of twelve possible words. Each sentence may be read aloud up to two times. The partner must transcribe each sentence on a standardized form. A survey will be provided to evaluate the "mask on, communicator on" period.

The audio recording will then be stopped.

At the end of this period, we will collect the communications devices. The survey collection will be optimized by medical record labels affixed to the surveys.

Audio recordings will be then evaluated by impartial judge(s), again graded for both single word and sentence readings. Once the data has been collected, the dataset will then be de-identified and stored for further analysis.

5. Study Population

a) Number of Subjects

The study intends to include approximately 30 volunteer subjects in a 2:1 assignment, across all hospital systems. This study is intended to be held at Grady Memorial Hospital / Emory University Hospital / Emory Midtown / Executive Park 12 (Brain Health).

b) Inclusion and Exclusion Criteria

Inclusion

Patients must be receiving BPAP/CPAP therapy in the outpatient setting (e.g. clinics, sleep centers).

Version Date: 27 Mar 2019

Exclusion

Patients cannot be intubated or have a tracheostomy.

No vulnerable populations will be included (children, decisionally impaired adults, and prisoners).

Patients cannot have speech disabilities, or reading disabilities, dyslexia.

Partners cannot have speech disabilities, hearing disabilities, reading disabilities, or writing disabilities.

English must be their first language.

c) Vulnerable Populations

- 1. Children: will be excluded
- 2. Pregnant women: will be included given minimal risk
- 3. Decisionally impaired adults: will be excluded
- 4. Prisoners: will be excluded

d) Setting

Recruitment, consent process, and equipment administration will be performed by study coordinators or study staff at each location.

Initial data collection will be performed by study staff. Study staff may also participate in blinded data evaluation.

Emory/Grady will not be the coordinating center for any activities.

All sites will rely on the Emory IRB as a first IRB review. Each location will have their own research committee for further review.

Grady

We will apply to the Grady research oversight committee.

Emory Healthcare

We will apply to Emory research administration.

e) Recruitment Methods

Patients will be recruited from clinics involved in BPAP/CPAP therapy. Potential subjects will be identified by their use of BPAP/CPAP therapy as a form of NIPPV. We will advertise by posting signs in clinic rooms and waiting rooms. Additionally, a study staff member may approach

patients waiting in the clinic rooms to inform them about the study. Finally, a study staff member may call patients scheduled for upcoming appointments. Subjects (patients, family/friends, staff) will be asked to volunteer. We will offer \$25.00 to each patient and partner in compensation (\$50.00 total for each pair) in cash after completion of the full study protocol. The price of the communicator will be covered by Ataia, Inc. The devices will remain the property of Ataia, Inc. and will not be given to the patients.

f) Consent Process

Consent will be obtained upon arrival and agreement to participate in the study. Consent will be confirmed via the patient's or partner's signature on the consent form. The subject will be given an explanation of how the device is used and the benefits of participating in the study. The patient will be informed that if at any time they revoke consent, to inform the physician, respiratory therapist, nurse, or study coordinator.

6. Procedures

- 1. Patient is treated by a sleep specialist with BPAP/CPAP.
- 2. Study information and informed consent provided.
- 3. If accepted, a study communications device will be attached to the BPAP/CPAP machine.
 - a. The standard of care does not have any kind of communications device attached to the mask. At the discretion of the clinical staff, communication boards or white boards may be provided.
 - b. There are two separate arms in this study. The patient will be randomly assigned:
 - i. to receive a non-functioning study communications device.
 - ii. to receive a functioning study communications device.
- 4. All patients involved in the study will have their medical record number recorded for further chart review.
- 5. The patient and partner will be briefed by the study coordinator. Patient and partner demographics data will be collected at the time of consent.
- 6. The patient will meet with study staff to conduct the trial.
 - a. Study coordinator will calibrate ambient speaker to desired loudness, as measured by decibel meter. Study coordinator will also calibrate other equipment for the trial.
 - b. Patient and partner will be situated in a standard setting. A microphone will be set up adjacent to the partner.
 - c. Example words and sentences will be provided to the patient and partner to practice protocol. No post-example survey will be provided at this stage.
 - d. Words and sentences will be provided to the patient and the partner to learn how intelligible the patient is at baseline, without the BPAP/CPAP mask on. The patient will read each of the words and sentences at most twice total and the guest will attempt to either identify or write down what is heard.
 - e. A survey will be provided to evaluate the "mask off" stage

- f. The patient will then wear the BPAP/CPAP mask without the communicator and turn on the BPAP/CPAP machine. Patient will be instructed to use their home settings.
- g. Patients will be asked to speak normally with the same volume and effort they used in the mask off phase.
- h. The partner will subsequently ask the patient to read a new set of trial words and sentences, with the partner again trying to identify or write down the spoken content. During this period, the study coordinator will show a sign to the patient to remind them to avoid overenunciating or overpronouncing words, and to avoid raising their voice.
- i. The patient will subsequently read a new set of words and sentences, with the guest again trying to identify or write down the spoken content.
- j. A survey will be provided to evaluate the "mask on, communicator off" stage
- k. The patient will then wear the BPAP/CPAP mask, with the communicator attached.
- I. The patient will subsequently read a new set of words and sentences, with the guest again trying to identify or write down the spoken content.
- m. A survey will be provided to evaluate the "mask on, communicator on" stage
- 7. Chart review of the patients.
- 8. Study judges blinded to the phase and study arm will transcribe the recorded audio.

7. Data and Specimens

Sharing of Results with Subjects

No lab tests or genetic tests will be performed. Study results will not be shared with subjects or their providers.

8. Data Analysis

Two-tailed parametric tests will be performed on the de-identified data to compare each arm to determine superiority. The primary goal of this study is to determine effect size and observe device usage.

Likert scales will be compared across patients and partners using a nonparametric test.

Randomization

Block randomization will be used with variable block sizes of three and isx. This guarantees that the 2:1 ratio is closely maintained througout the trial. Sealed envelopes will be utilized, with "disable" being the placebo and "enable" being the treatment. The subjects are numbered from 1 to 42. If we randomize only 30 subjects, we will have 20 enable and 10 disable. If we have 30 subjects, then the power is 70%.

Interim analysis

One interim analysis will be undertaken after fifteen subjects are evaluated for the primary pre-Version Date: 27 Mar 2019 Page 10 of 13

post outcome. The O'Brien-Fleming stopping rule will be used with a Type I error rate of 0.05.

9. Privacy, Confidentiality and Data Security

All subjects will be assigned a study ID. Subject forms will be organized with medical record stickers for ease of use. Data collation and chart review will then be performed by authorized personnel.

During chart review, we will gather relevant clinical history, including but not limited to previous diagnoses (especially COPD or asthma), duration of BPAP/CPAP therapy, and any factors that may impair patient communication. Additionally, incidental relevant possible or probable complications will be recorded.

Once data collation and chart review has been completed, the data shall be de-identified and referred for statistical analysis.

All data will be encrypted, regardless of identified or de-identified. Certificates of confidentiality and other paperwork shall be stored in a secured location by authorized personnel.

10. Risks and Benefits

a. Risks to Subjects

This study involves a new device that assists in communication for patients requiring BPAP/CPAP, and does not disrupt the function of the BPAP/CPAP. The device will not be in direct contact with the patient. Based on its design, it is unlikely to interrupt BPAP/CPAP functionality. There are no additional lab tests or imaging that should be required to participate in this study. There may be other risks, discomforts, and side effects that are not yet known.

It is unlikely that a survey will pose any risk. It is further unlikely that recorded audio of provided words and sentences will pose any risk.

Chart review will be performed by approved personnel to further quantify side effects. Reviewed data will be de-identified prior to further analysis.

We will provide a mask and hose to the patient for the duration of this trial. It is unlikely that a standard single-use CPAP/BPAP mask will pose any risk for the duration of the trial.

For the duration of the trial, we will provide a constant pressure of 10 cm H2O when on NIV. It is unlikely that this pressure will pose any risk for the duration of the trial.

The patch, designed to adhere to the mask, is also designed to be completely removable within the first 8 hours after application. We will be able to remove any unwanted adhesive residue. In

the event that the patient's mask is unable to function in the original condition once the patch is removed, as per determined by the study staff, we will be able to replace the mask.

i. Adverse events

In the event that an adverse event occurs, the study staff conducting the experiment will record the circumstances. These forms will be submitted to the co-investigator and/or PI for review. Adverse event forms will be reviewed weekly.

These forms will also be sent to the Ataia Medical Quality officer.

b. Potential Benefits to Subjects

Taking part in this research may, if on the intervention arm, potentially benefit the patient and those interacting with the patient by facilitating communication. If assigned to the control arm of the study, there may be no direct benefit to the patient from taking part in this study. However, this research study may help us learn new things that may help patients in the future.

11. Disclosures

[name] has developed IP that has been released to Ataia Medical, a company interested in further developing the IP that is the subject of this publication. [name] serves as Chief Medical Officer and has ownership interests in Ataia Medical. The terms of this arrangement have been reviewed and approved by Emory University in accordance with its conflict of interest policies.

References

- Confalonieri, M. *et al.* Noninvasive mechanical ventilation improves the immediate and long-term outcome of COPD patients with acute respiratory failure. *Eur. Respir.* J. **9**, 422–430 (1996).
- Centers for Disease Control and Prevention (CDC). Chronic obstructive pulmonary disease among adults--United States, 2011. *MMWR Morb. Mortal. Wkly. Rep.* 61, 938–943 (2012).
- 3. Perera, P. N., Armstrong, E. P., Sherrill, D. L. & Skrepnek, G. H. Acute exacerbations of COPD in the United States: inpatient burden and predictors of costs and mortality. *COPD* **9**, 131–141 (2012).

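### The block sizes are printed in the protocol used by the staff who recruit, consent and set the device, so past allocations partly reveal coming ones: a modest risk that is cheap to remove

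*Combined protocol and SAP*

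**What the plan says.** Section 4 (Study Design) states: "Block randomization will be used with variable block sizes of three and six". The Randomization paragraph of Section 8 says the same with a typing error: "Block randomization will be used with variable block sizes of three and isx". The stated purpose is balance: "This guarantees that the 2:1 ratio is closely maintained throughout the trial". On list length and split the plan says "The subjects are numbered from 1 to 42" and "If we randomize only 30 subjects, we will have 20 enable and 10 disable".

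On concealment it says only "Sealed envelopes will be utilized". It does not say who prepares or holds the envelopes, when each is opened, or whether the sites share one list. Nothing says that the block sizes are withheld from enrolling staff.

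On roles, Section 4 first says "The study consenter will turn the device on if randomized to the" communicator arm, and that the same person disables it otherwise. The later account of the session in Section 4 gives this step to the study coordinator. Section 5d assigns recruitment, consent and equipment administration to coordinators or study staff at each of the named locations. Section 5e lets staff approach patients in clinic, and adds that "a study staff member may call patients scheduled for upcoming appointments". The trial is single-blinded.

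**The concern.** A sealed envelope hides its own contents, but not what can be deduced from the envelopes already opened. In 2:1 blocks as short as three, someone who knows the sizes and the recent allocations can often form a strong view of the next one. Here the people with that knowledge may also decide whom to approach or telephone. If they expected enable next, they could, knowingly or not, favour a pair that is likely to do well.

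With about 10 controls planned, the comparison has little room to absorb selection. Section 11 discloses an ownership and officer interest in the device company. That is not evidence of steering, but it is a reason for concealment not to rest on trust.

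**Working it through.** **Inputs from the protocol.** Block sizes 3 and 6; ratio 2:1 enable to disable; list of 42; planned 30 as 20 and 10; four named locations.

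**Assumptions.** The mix of sizes is not stated. Equal odds are the base case, with the share of size-3 blocks varied from 25% to 75%. The observer knows the two sizes and every earlier allocation, but not the order of the sizes.

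**Step 1: the plan's own split.** In 20,000 simulated lists, 30 subjects gave exactly 20:10 in 87% (84% to 92% over the range of mixes), and otherwise 19:11 or 21:9. The stated split is reproduced as the usual result. It is not guaranteed, because a block of six can straddle subject 30.

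**Step 2: the forecast by hand.** For the first block, with equal odds of 3 (two enable, one disable) and 6 (four enable, two disable):

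- After a first disable: both sizes give a first disable with probability 1/3, so they stay equally likely. P(next enable) = 0.5 × 1 + 0.5 × 4/5 = 0.90.
- After enable, enable: the likelihoods are 2/3 × 1/2 = 1/3 (size 3) and 4/6 × 3/5 = 2/5 (size 6), so P(size 3) = (1/3)/(1/3 + 2/5) = 5/11. P(next disable) = 5/11 × 1 + 6/11 × 2/4 = 8/11 = 0.73.
- After two disables among the first three: size 3 is ruled out and both disables are spent, so the next allocation is enable with certainty.

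**Step 3: the whole sequence of 30.** The same Bayesian update, applied at each allocation:

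| Share of size-3 blocks | Certain | At least 80% predictable | Best guess right | Disables guessed |
|---|---|---|---|---|
| 25% | 12.8% | 40.6% | 74.6% | 35% |
| 50% | 9.7% | 39.3% | 75.3% | 35% |
| 75% | 5.7% | 46.4% | 76.4% | 35% |

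In the base case 0.097 × 30 = 2.9 allocations are certain (5th to 95th percentile 0 to 8), and 0.393 × 30 = 11.8 are at least 80% predictable. Always guessing enable is right 66.7% of the time, so the gain is 75.3 − 66.7 = 8.6 percentage points. Only 2.1% of allocations are a certain disable. A forecast of disable is made about 4.4 times in 30 and is right about 0.35 × 10 / 4.4 = 80% of the time.

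**Step 4: one list over four sites.** If four equal sites draw from one list and staff see only their own allocations, 0.2% are certain, 8% are at least 80% predictable, and the best guess is right 67% of the time, no better than the ratio alone. A separate list at each site would bring the predictability back.

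**Step 5: longer blocks.** For an observer who knows the sizes, blocks of 6 and 9 instead of 3 and 6 change the certain share from 10% to 5%, the share at least 80% predictable from 39% to 35%, correct guesses from 75% to 73%, and disables guessed from 35% to 34%. Splits other than 20:10 at 30 rise from 13% to 26%. Length alone buys little; most of the benefit must come from not disclosing the sizes.

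**The case against.** A reader might infer a large, quantified bias. If every forecast above or below 2/3 shifted the analysed outcome by ±0.25 SD, the bias would be about 0.22 SD and the Type I error about 8.0%; at ±0.5 SD, about 0.43 SD and 15.9%. The documents do not support that reading, for three reasons.

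- **Amount of steering.** It needs steering on about 71% of pairs, or 21 of 30. If staff acted on a tenth of those forecasts (about two pairs), the bias would be 0.02 to 0.045 SD and the Type I error about 5%. Acting on a quarter gives 5.3% to 5.8%.
- **Outcome.** It adds the shift straight to the analysed outcome. Sections 4 and 8 call the primary outcome pre-post, and each pair is scored without the mask and with the mask alone before the device is set. A clear speaker scores higher in all phases. With additive scores and clarity carrying 0.5 or 0.7 of the variance (assumed), a change score keeps the Type I error at about 5% for both shifts. Baseline adjustment gives about 5% to 7%, rising to about 8% at the least favourable setting (share 0.5, ±0.5 SD).
- **Observer.** It needs one enroller who sees the whole list. The single numbering from 1 to 42 reads like one shared list over four locations, in which case the forecast is nearly worthless.

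It would also be too strong to say that most allocations can be foreseen: about one in ten is certain, and most confident calls are enable, which is already 67% likely.

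These points limit the harm but do not remove the weakness. The protocol does not define the pre-post analysis, does not say whether the list is shared, and describes no safeguard beyond the envelopes.

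**Conclusion.** The concealment weakness is real and modest. For one enroller who sees the whole list, about 10% of allocations are certain and about 39% are at least 80% predictable, with 75% of guesses right against 67%. These figures rest on equal odds of the two sizes and on knowledge of all earlier allocations; they fall close to nothing under a shared four-site list with site-only knowledge. The size of any bias is unknown, and no inflated Type I error should be quoted as a property of this trial. Nothing in the documents suggests that steering has happened. Severity is minor: the reason to act is that the risk is avoidable at almost no cost.

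**What to change.** 1. Delete the block sizes from Sections 4 and 8. State that they are held only by the person who makes the list.
2. Because the current sizes are already known, regenerate the unused envelopes with undisclosed, randomly varied sizes. The choice of sizes can be left to the statistician.
3. Enter each consented pair on a sequentially numbered log before its envelope is opened, and delay opening until the mask-off and mask-only phases are complete.
4. State who holds the envelopes and whether there is one list or one per site, and reconcile the two statements in Section 4 on whether the consenter or the coordinator sets the device.

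The cost is regenerating a short list (42 at most), a paper log, and edits to two paragraphs, with no extra staff or subjects. If longer blocks are chosen, a split other than 20:10 at 30 becomes somewhat more likely (with 6 and 9, 26% against 13%), with trivial loss of power.

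### The primary pre-post outcome has no named score, rater, 'pre' phase or model: name them and prespecify ANCOVA on the mask-on, no-communicator score (gain conditional on an unstated correlation)

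*Combined protocol and SAP*

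**What the plan says.** Section 8 (Data Analysis) gives the between-arm analysis in one sentence: "Two-tailed parametric tests will be performed on the de-identified data to compare each arm to determine superiority". It names no test, covariate or outcome. The primary outcome is mentioned only in the interim-analysis text of Section 4, repeated in Section 8: "One interim analysis will be undertaken after fifteen subjects are evaluated for the primary prepost outcome". An O'Brien-Fleming rule at a type I error of 0.05 applies to it. The plan gives 70% power for 30 subjects (20 enabled, 10 disabled) without an effect size, SD, correlation or test.

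Several measurements could be this outcome:

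- **Score.** In each phase the partner picks words from a list of twelve and also transcribes sentences.
- **Rater.** Besides the partner, "Audio recordings will be then evaluated by impartial judge(s), again graded for both single word and sentence readings".
- **'Pre' phase.** Step 6d of Section 6 uses the mask-off phase "to learn how intelligible the patient is at baseline, without the BPAP/CPAP mask on". Step 6f adds a second scored phase before the device is attached: "The patient will then wear the BPAP/CPAP mask without the communicator and turn on the BPAP/CPAP machine".

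For phase 3, Section 4 says "A new list of single words and 5-word through 15-word sentences will be provided to the patient". At that point the communicator is enabled or disabled according to arm.

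**The concern.** A superiority test, a power figure and a stopping boundary each need one defined statistic. Here the analyst could settle the score, rater, reference phase and model after seeing the data, including at the interim look. That weakens the 5% error rate. It also leaves the effect size, whose estimation Section 8 calls part of the primary goal, without a defined contrast.

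Precision is also at stake. With 20 against 10 subjects the choice of model can matter, and the phase 2 score (mask on, no communicator) is already being collected.

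Phase 2 can serve as 'pre' only if allocation cannot influence it. Section 4 sets the device after phase 2, but Section 6 lists device attachment and random assignment at step 3, ahead of all the phases in step 6. No passage says when the envelope is opened. In phase 2 the coordinator also prompts the patient's speech: "During this period, the study coordinator will show a sign to the patient to remind them" not to raise the voice or over-enunciate.

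**Working it through.** **Inputs from the plan:** 20:10 allocation, two-sided 0.05, 70% power, interim after 15. **Assumed, because the plan does not give them:** pre-post correlation rho = 0.3/0.5/0.7/0.8 (also 0), k = pre SD / post SD = 0.7, 1 or 1.3, roughly normal scores and no dropout.

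**1. Readings of the outcome.** 2 scores × 2 raters × 2 'pre' phases = 8. If any could be claimed at 0.05, the chance of at least one false positive would be 1 − 0.95^8 = 33.7% if independent, and about 16% at a common correlation of 0.8. This only illustrates scale; the real correlations are not given.

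**2. The stated 70%.** It cannot be reproduced without an effect size and SD. Solving backwards for a two-sample t-test (28 df, noncentrality d/√(1/20 + 1/10)) gives d = 0.997 SD. This is used below only for calibration.

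**3. Half-width of the 95% CI, in phase 3 SDs.**
- Phase 3 alone: t(28) × √0.15 = 2.048 × 0.387 = 0.793.
- Change: 0.793 × √(1 + k² − 2·rho·k).
- ANCOVA: t(27) × √(0.15 × (1 − rho²) × 27/26), for any k.

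| rho | 0.3 | 0.5 | 0.7 | 0.8 |
|---|---|---|---|---|
| ANCOVA | 0.773 | 0.701 | 0.578 | 0.486 |
| Change, k = 0.7 | 0.821 | 0.705 | 0.567 | 0.483 |
| Change, k = 1 | 0.939 | 0.793 | 0.615 | 0.502 |
| Change, k = 1.3 | 1.096 | 0.935 | 0.740 | 0.620 |

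The largest excess of ANCOVA over the better unadjusted test is at rho = 0: 0.810 − 0.793 = 0.017 in half-width, about 0.03 in full width.

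**4. Final power, with the change-score t-test set at 70%** (simulation, 100,000 trials per cell).

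| rho | 0.3 | 0.5 | 0.7 | 0.8 |
|---|---|---|---|---|
| ANCOVA, k = 1 | 85.5% | 80.3% | 75.2% | 72.9% |
| ANCOVA, k = 0.7 | 75.2% | 70.4% | 68.5% | 69.3% |

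At k = 0.7 there is in effect no gain over change from rho = 0.5 up. At k = 1 and rho = 0.3 a phase 3-only test would have 83.5%, so most of that gain is over the change score. The worst final loss against the better unadjusted test is 1.7 points.

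**5. False-positive rate for one score, no device effect.** Each test alone holds about 5%. Claiming whichever of change and ANCOVA is significant gives, over rho = 0.3 to 0.8, about 6.5–7.8% at k = 1 and 5.7–6.8% at k = 0.7. A rerun of the same simulation at k = 1.3 gives about 8%. Allowing a phase 3-only test as well gives 8.2–9.3% at k = 0.7, 9.2–10.3% at k = 1 and 9.9–11.6% at k = 1.3.

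**6. Interim cost.** At 10:5 ANCOVA has 12 df instead of 13. At the O'Brien-Fleming level of 0.0052 (interim at half the information), the worst losses against the better unadjusted test are 40.4 − 36.9 = 3.5 points (k = 0.7, rho = 0.8, phase 3-only test set at 70%) and 40.3 − 35.5 = 4.8 points (k = 1.3, rho = 0, change set at 70%). Over both looks the worst loss is 69.8 − 68.0 = 1.8 points.

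**7. Bounded scores.** With 10 or 20 items assumed, and up to 45% of enabled pairs at ceiling or 17% of pre scores at floor, ANCOVA's type I error was 4.7–5.1%. Its power ran from 1.2 points below to 18.6 above the better unadjusted test.

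**The case against.** Five points can be made for the plan.

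- **The word pre-post already limits the choice.** A test on phase 3 alone uses no pre score. A reader might infer a false-positive rate of 9–10% or more, but that counts such a test, which the plan's own term disfavours. This stands: change against ANCOVA is the fair comparison.
- **ANCOVA is partly a preference.** Any single prespecified pre-post model, including phase 3 minus phase 2, removes the after-the-fact choice. This stands. ANCOVA rests on precision, which depends on rho and k.
- **The study is partly exploratory.** Its stated goal is to estimate the effect and see how the device is used. That softens the standard, but the plan also claims superiority, power and an alpha-controlled stopping rule, and an effect estimate needs a defined contrast in any case.
- **Phases 2 and 3 may be more alike than they look.** The practice period and reminder sign are described only for phase 2, but Section 4 says the protocol is unchanged in phase 3, which may carry the speaking instructions forward. The word lists are new either way. This does not affect the case for a covariate.
- **Pressure is a separate matter.** Step 6f says "Patient will be instructed to use their home settings", whereas Sections 4 and 10 state a constant 10 cm H2O. These passages must be reconciled, but no passage changes pressure between phases 2 and 3, so the conflict does not bear on the model.

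**Conclusion.** The gap is real and should be closed, though it is not fatal. No part of the plan fixes the score, rater, 'pre' phase or model. For one score, open choice between two pre-post models costs about 1.5 to 3 points of type I error at k = 1 and 1 to 2 points at k = 0.7. Choice among scores, raters and phases would add an amount that the documents do not let us determine.

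ANCOVA on the phase 2 score is the better default because its worst final loss is about 2 points and its possible gain is larger, and the sponsor cannot know beforehand which unadjusted test would do better. It is not uniformly superior: the gain over change vanishes at k = 0.7 from rho = 0.5 up.

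A reader might also infer that the 70% is wrong or that the planned comparison is biased. The documents support neither. The 70% can be neither confirmed nor refuted, and randomization protects a comparison of the arms, provided allocation stays hidden until phase 2 is scored when that score is used. All figures rest on assumed rho and k and roughly normal scores, with bounded scores checked only under assumed item counts.

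**What to change.** In Section 8:

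1. Name one primary score and one rater, and state that 'pre' is phase 2.
2. Add: 'The arms are compared on the phase 3 (communicator attached) score by ANCOVA with the phase 2 (mask on, no communicator) score as covariate. The effect size is the adjusted enabled-minus-disabled difference with its 95% CI. The same model is used at the interim analysis.'
3. State the effect size, SD and test behind the 70%.

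In Sections 4 and 6, state that the envelope stays sealed until phase 2 scoring is finished, and bring the order of step 3 into line with this.

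If the sponsor prefers a change score, prespecifying phase 3 minus phase 2 also closes the after-the-fact choice, with the precision tabulated above.

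The cost is a few lines of text and no new data. ANCOVA uses one degree of freedom (27 instead of 28 at the end, 12 instead of 13 at the interim) and may slightly reduce the chance of stopping early.
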